1.3.2 Randomization	
Randomization Type:	 Open-Label  Single Blind  Double-Blind
1.4 Timing of Analysis	
Planned Interim Analysis	 Cohort Review / Dose Escalation  Safety Review  Interim Efficacy/Safety Analysis  Independent DMC/DSMB  Annual Report / Investigator Brochure (IB)  Abstract / Scientific Presentation (Oral/Poster)
Final Analysis	As determined by the Study Chair in consultation with the clinical team

1.5 Responsibilities	
Trial Statistician:	Prepare SAP checklist and TFL shells. Review deliverables produced by Statistical Programmers.
PK Statistician:	N/A
Independent Statistician:	N/A
1.6 Analysis Software	
Main statistical analysis:	SAS Version 9.3 or above
Other analysis software:	N/A

1.7 Coding	
 Adverse Events  Medical History	 MedDRA:  Version  Most current release and update coding with new major releases  NCI-CTCAE Version v4.0
 Concomitant Medication  Prior Therapy  Subsequent/Further Therapy	 WHO-Drug:  Version  Most current release and update coding with new major releases
3 Analysis Population	
Intent-To-Treat (ITT) Population definition:	 All patients who have started treatment in the study  All patients who have been randomized in the study, regardless of whether they have received any treatment or not  All patients who have been randomized and have started treatment in the study  Other definition, specify:
Per Protocol (PP) Population to be used in analysis:	 Yes  No If yes, please specify the criteria for exclusion from the PP population:
Safety (SAF) Population definition	 The Safety population will consist of all patients who received at least one dose of MLN9708.  Other definition, specify:
Other Analysis Population definition:	The Efficacy Evaluable population will consist of all patients with measurable or evaluable disease at baseline who receive at least 1 dose of MLN9708 and undergo at least one post-baseline disease assessment. In addition, patients who discontinued the study prior to their first post-baseline disease assessment due to death or progressive disease will also be included in the Efficacy Evaluable population.
4 Baseline Value Definitions	
	Information collected and procedures performed for each patient at ≤7 days prior to initiation of treatment.
5/6 Efficacy	
Response Criteria Used:	 RECIST 1.0  RECIST 1.1  Cheson 2007  Modified RECIST – specify:  Other criteria, Specify: International Myeloma Working Group Uniform Response Criteria
Efficacy Assessment Timepoints:	Patients will be re-evaluated for response to treatment after 2 cycles of treatment. Response will be assessed at 8-week intervals (±1 week) during study treatment. Patients with progressive disease (PD) or unacceptable toxicity should be discontinued from the study; patients with stable disease (SD) or response to therapy will continue treatment through 6 cycles.

Efficacy Endpoints:	
  
 	Endpoint	Primary Analysis Population	Other Analysis Population	
   
 Primary	PFS	Efficacy Evaluable		
 
 Secondary	OS	Efficacy Evaluable		
  
		Endpoint	Primary Analysis Population	Other Analysis Population	Primary	PFS	Efficacy Evaluable		Secondary	OS	Efficacy Evaluable							
	Endpoint	Primary Analysis Population	Other Analysis Population																
Primary	PFS	Efficacy Evaluable																	
Secondary	OS	Efficacy Evaluable																	
Definition of Terms:																			
 Response	 Complete Response + Partial Response as best observed response  Complete Response + Partial Response, confirmed with _____ weeks apart.  Other criteria, specify: International Myeloma Working Group Uniform Response Criteria: sCR (stringent complete response) CR (complete response) VGPR (very good partial response) PR (partial response) SD (stable disease) PD (progressive disease)																		
 Clinical Benefit	 Complete Response + Partial Response + Stable Disease as best observed response  Complete Response + Partial Response (confirmed with _____ weeks apart) + Stable Disease (at least _____ weeks from start of treatment)  Other criteria, specify:																		
 Progression	As reported by Investigator																		
 Subsequent Therapy																			
 Treatment Failure																			
Definition of Endpoints:	Start Date:  Date of Randomization  Date of First Treatment End Date (specify for all pertinent endpoints): Progression-Free Survival: Event = Progression or Death 
  
 Situation	Date of Event or Censoring	Outcome	
   
 No baseline assessment	Date of first treatment	Censored	
 
 PD documented between scheduled visits, did not die, and received no subsequent therapy	First date of evaluated overall response = PD	Event	
 
 PD documented between scheduled visits, did not die, but received subsequent therapy prior to incurring progression event	Date of last evaluable tumor assessment prior to start of subsequent therapy	Censored	
 
 Death while on-study without previous PD, and received no subsequent therapy	Date of death	Event	
 
 Death while on-study and had previous PD, and received no subsequent therapy	First date of evaluated overall response = PD	Event	
  
	Situation	Date of Event or Censoring	Outcome	No baseline assessment	Date of first treatment	Censored	PD documented between scheduled visits, did not die, and received no subsequent therapy	First date of evaluated overall response = PD	Event	PD documented between scheduled visits, did not die, but received subsequent therapy prior to incurring progression event	Date of last evaluable tumor assessment prior to start of subsequent therapy	Censored	Death while on-study without previous PD, and received no subsequent therapy	Date of death	Event	Death while on-study and had previous PD, and received no subsequent therapy	First date of evaluated overall response = PD	Event
Situation	Date of Event or Censoring	Outcome																	
No baseline assessment	Date of first treatment	Censored																	
PD documented between scheduled visits, did not die, and received no subsequent therapy	First date of evaluated overall response = PD	Event																	
PD documented between scheduled visits, did not die, but received subsequent therapy prior to incurring progression event	Date of last evaluable tumor assessment prior to start of subsequent therapy	Censored																	
Death while on-study without previous PD, and received no subsequent therapy	Date of death	Event																	
Death while on-study and had previous PD, and received no subsequent therapy	First date of evaluated overall response = PD	Event																	

	Death while on-study without previous PD, but received subsequent therapy prior to death event	Date of last evaluable tumor assessment prior to start of subsequent therapy	Censored
	Death while on-study and had previous PD, but received subsequent therapy prior to PD event	Date of last evaluable tumor assessment prior to start of subsequent therapy	Censored
	No progression, no death	Date of last evaluable tumor assessment	Censored
	Treatment discontinuation for adverse event or other non-event reason	Date of last evaluable tumor assessment	Censored
Overall Survival: Event = Death			
	Situation	Date of Event or Censoring	Outcome
	Death, while on-study or follow-up	Date of death	Event
	Alive, as of end of study or follow-up	Date last known alive	Censored
	Status unknown, as of end of study	Date last known alive	Censored
 Overall Response Rate (ORR)	Default: Estimates of rates in each treatment arm		
 Disease Control Rate (DCR)	 Difference in rates & 95% confidence interval between treatment arms		
 Clinical Benefit Rate (CBR)	 p-value, specify statistical test:		
 Early Progression Rate (EPR)			
 Time To Progression (TTP)	Default: Estimates of medians in each treatment arm		
 Progression-Free Survival (PFS)	 Other quartiles or percentages of survival required, specify: PFS, OS: 2 year PFS and OS with 95% confidence intervals		
 Overall Survival (OS)	 Hazard ratio & 95% confidence interval between treatment arms, unstratified		
 Duration of Response	 p-value, specify statistical test:		
 Duration of Stable Disease	 Hazard ratio & 95% confidence interval between treatment arms, stratified (specify stratification factor(s)):		
 Time To Treatment Failure (TTF)	 p-value, specify statistical test:		
 Other, Specify:			
7 Safety			
Adverse Events	Definition of Treatment-Emergent Adverse Event (TEAE): Treatment-emergent AEs are those with an onset on or after the initiation of therapy, and will be graded according to NCI CTCAE v4.0.		
Laboratory Data	Data will be summarized by:  NCI-CTCAE for CTCAE-gradable parameters, and H/L for non-CTCAE-Gradable parameter  H/L for all lab parameters		

Tier 1 Study – Tables, Figures & Listings

Standard TFLs			
Table No	Description	Variables/Analyses To Be Included	Subgroup Analyses
Table 1	Summary of Patient Disposition	 Number of patients screened  Number of patients randomized  Number of patients treated  Reason for treatment discontinuation  Reason for study withdrawals  Other, specify: Patient Deaths; Time on Study	
Table 2	Summary of Demographic Characteristics	 Age: Mean, SD, Median, Min, Max  Age Group:  Sex  Race  ECOG  Other, specify:	
Table 3	Summary of Disease History	 Histology  Disease Staging  Time from Diagnosis  Other, specify: Baseline FISH Baseline Cytogenetics	
Table 4	Summary of Patient Treatment and Dose Modifications (reductions, interruptions)		
Table 5	Summary of Grade 3+ Adverse Events		
Table 6	Summary of Treatment-Related Grade 3+ Adverse Events		
Table 7	Summary of Serious Adverse Events		
Table 8	Summary of Treatment-Related Serious Adverse Events		
Table 9	Summary of Treatment Related Adverse Events Leading to Death		
Table 10	Summary of Best Overall Response		
Table 11	Summary of Response Over Time		
Table 12	Summary of Progression-Free Survival (Kaplan-Meier estimates & 95 CI)		
Table 13	Summary of Overall Survival (Kaplan-Meier estimates & 95 CI)		
Table 14	Summary of Adverse Events with \geq 5% Frequency (for: CTGOV)		

Figure No	Description	Variables/Analyses To Be Included	Subgroup Analyses
Figure 1	Progression-Free Survival	Timescale to be used on horizontal axis:  Day  Week  Month  Year	
Figure 2	Overall Survival	Timescale to be used on horizontal axis:  Day  Week  Month  Year	

Listing No.	Title	Variables/Analyses To Be Included	Subgroup Analyses

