3. STUDY PATIENT POPULATION AND DISCONTINUATION

3.1 Inclusion Criteria

Patients must meet the following criteria in order to be included in the research study:

1. Symptomatic multiple myeloma or asymptomatic myeloma with myeloma-related organ damage diagnosed according to standard criteria in patients who received allogeneic transplant due to high-risk prognostic features, such as, but not limited to:
 - Chromosome 17p, partial deletion (del(17p), t(4;14), t(14;16), t(14;20)
 - Plasma cell leukemia
 - Progression-free survival of less than 2 years after autologous stem cell transplant

CONFIDENTIAL

STUDY DRUG: MLN9708
FINAL PROTOCOL: 11 APRIL 2014
AMENDMENT NUMBER 3: 11 FEBRUARY 2016

SCRI INNOVATIONS STUDY NUMBER: MM 42

VERSION 4

2. Evidence of engraftment of neutrophils (absolute neutrophil count [ANC] >1000 cells/mm³) and platelets (platelets >60,000 cells/mm³ [dose escalation phase] and >50,000 cells/mm³ [dose expansion phase])
3. Achievement of at least a PR prior to allogeneic stem cell transplant.
4. Adequate liver function defined as:
 - Alanine aminotransferase (ALT) and aspartate aminotransferase (AST) ≤3.0 x the upper limit of normal (ULN)
 - Total bilirubin ≤2.0 x ULN
5. Adequate renal function defined as creatinine clearance ≥30 mL/min, estimated or calculated.
6. Aged ≥18 and ≤70 years, at time of enrollment
7. Ability to swallow oral medication
8. Absence of gastrointestinal symptoms that precludes oral intake and absorption of MLN9708 (nausea, vomiting, diarrhea, malabsorption)
9. Off antibiotics and amphotericin B formulations, voriconazole or other anti-fungal therapy for the treatment of proven, probable or possible infections (defined in accordance with the European Organization for Research and Treatment of Cancer/Invasive Fungal Infections Cooperative Group and the National Institute of Allergy and Infectious Diseases Mycoses Study Group [EORTC/MSG] criteria)
10. Eastern Cooperative Oncology Group (ECOG) Performance Status score of ≤ 2 (Appendix A)
11. Life expectancy ≥3 months
12. Male patients with female partners of childbearing potential and female patients of childbearing potential are required to use two forms of **acceptable** contraception, including one barrier method, during their participation in the study and for 90 days following last dose of study drug. Male patients must also refrain from donating sperm during their participation in the study (Appendix C).

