3.2 Exclusion Criteria

Patients who meet any of the following criteria will be excluded from study entry:

3. Patients who have progressive disease when compared to pre-transplant staging as defined by IMWG Uniform Response criteria for Multiple Myeloma (see Appendix E).
4. Umbilical cord blood transplant

5. Patients with > Grade 2 peripheral neuropathy with pain, or \geq Grade 3 peripheral neuropathy per National Cancer Institute Common Terminology Criteria for Adverse Events (NCI CTCAE) Version 4.0
6. Patients with uncontrolled bacterial, viral, or fungal infections
7. New York Heart Association (NYHA) Class III or IV heart failure uncontrolled angina, severe uncontrolled ventricular arrhythmias, or electrocardiographic evidence of acute ischemia or active conduction system abnormalities (see Appendix B). Prior to study entry, any electrocardiogram (ECG) abnormality at Screening has to be documented by the Investigator as not medically relevant.
8. Patients who are pregnant (positive beta-human chorionic gonadotropin [β -HCG]) or breastfeeding
9. Most recent chemotherapy \leq 21 days and \leq Grade 1 chemotherapy-related side effects, with the exception of alopecia
10. Use of a study drug \leq 21 days or 5 half-lives (whichever is shorter) prior to the first dose of MLN9708. For study drugs for which 5 half-lives is \leq 21 days, a minimum of 10 days between termination of the study drug and administration of MLN9708 is required.
11. Wide field radiotherapy (including therapeutic radioisotopes such as strontium 89) administered \leq 14 days or limited field radiation for palliation \leq 7 days prior to starting study drug or has not recovered from side effects of such therapy
12. Major surgical procedures \leq 14 days of beginning study drug, or minor surgical procedures \leq 7 days. No waiting is required following port-a-cath placement.
13. Ongoing or active systemic infection. Known diagnosis of human immunodeficiency virus, hepatitis B, or hepatitis C
14. Central nervous system involvement
15. Known allergy to any of the study medications, their analogues, or excipients in the various formulations of any agent.

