10.3 Analysis Population

The following analysis populations will be used:

- The Safety population will consist of all patients who received at least one dose of MLN9708. This population will be used in all safety summaries.
- The Efficacy Evaluable population will consist of all patients with measurable or evaluable disease at baseline who receive at least 1 dose of MLN9708 and undergo at least one post-baseline disease assessment. In addition, patients who discontinued the study prior to their first post-baseline disease assessment due to death or progressive disease will also be included in the Efficacy Evaluable population.

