Appendix E: International Myeloma Working Group Uniform Response Criteria

Response Category	Definition

sCR Stringent Complete Response
	
CR criteria as defined below AND
 
 • Normal free light chain (FLC) ratio 
AND
 
 • Absence of phenotypically aberrant PCs in bone marrow^b analyzed by multiparametric flow cytometry

CR Complete Response
	
 • Negative immunofixation on the serum and urine 
AND
 
 • Disappearance of any soft tissue plasmacytoma(s) 
AND
 
 • $\leq 5\%$ plasma cells in bone marrow^b. • In case the only measurable disease in a patient with CR at baseline is the serum FLC level, a normal FLC ratio of 0.26 to 1.65 is required additionally to qualify for CR.

VGPR Very Good Partial Response
	
 • Serum and urine M-protein detectable by immunofixation but not by electrophoresis (PEP) or $\geq 90\%$ reduction from baseline serum) AND urine M-protein level < 100 mg/ 24h 
AND
 
 • In case of presence of soft tissue plasmacytoma(s) at baseline, disappearance of any soft tissue plasmacytomas 
In case the only measurable disease in a patient with VGPR at baseline is the serum FLC level (i.e. no measurable disease in serum and urine PEP), a decrease of $> 90\%$ in the difference between involved and uninvolved FLC levels from baseline is required.

PR Partial Response
	
$\geq 50\%$ reduction from baseline in serum M-protein
 
AND
 
$\geq 90\%$ reduction from baseline in 24h urinary M-protein OR urine M-protein < 200 mg/24h
 
If serum and urine M-protein are non-measurable at baseline, a $\geq 50\%$ reduction from baseline in the difference between involved and uninvolved FLC levels is required in place of the M-protein criteria.
 
If serum and urine M-protein are non-measurable, and serum free light assay is also non-measurable, $\geq 50\%$ reduction from baseline in percent plasma cells in bone marrow is required instead of M-protein measurement, provided baseline plasma cells in bone marrow was $\geq 30\%$.
 
AND
 
In case of presence of soft tissue plasmacytoma(s) at baseline, a reduction in the SPD by $\geq 50\%$ is required.

CONFIDENTIAL

STUDY DRUG: MLN9708
FINAL PROTOCOL: 11 APRIL 2014
AMENDMENT NUMBER 3: 11 FEBRUARY 2016

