1.2 Study Design	
Study Type	 Non-Randomized  Randomized (Allocation Ratio:)
Details	
This is a Phase II, open-label, multicenter, non-randomized study to determine the feasibility of MLN9708 as maintenance after allogeneic stem cell transplant for multiple myeloma. Patients will be enrolled between Days 45 and 120 after allogeneic transplant and will receive MLN9708 on Days 1, 8, and 15 of each 28-day cycle for 6 cycles. Up to 18 patients will be enrolled in the dose-escalation phase to define the MTD of MLN9708. An additional 20 patients will be enrolled in the expansion phase at the MTD.
 
PFS is defined as the time from the first day of study drug administration (Day 1) to disease progression as defined by the International Myeloma Working Group Uniform Response Criteria (see Appendix E of protocol), or death on study. Patients who are alive and free from disease progression will be censored at the date of last tumor assessment.
 
OS is defined as the time from the first day of study drug administration (Day 1) to death on study. Patients who are alive will be censored at the date of last known date alive.
 
PFS and OS (efficacy secondary endpoints) estimates will be generated using Kaplan-Meier methods, both for all patients enrolled and those patients receiving the MTD. Two-year PFS and OS estimates with 95% confidence intervals (CIs), and median PFS and OS with 95% CIs, will be generated and reported accordingly.

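### The SAP endpoint table puts PFS and OS on the Efficacy Evaluable set, but SAP 1.2 and the protocol say all enrolled; read plainly, the table leaves out patients in CR at entry

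*SAP*

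**What the plan says.** **Two populations for the same estimates.** SAP 1.2 says the Kaplan-Meier estimates of PFS and OS are produced "both for all patients enrolled and those patients receiving the MTD". Protocol 10.4.2 and the synopsis use the same words. In the SAP endpoint table (section 5/6), the primary population for both PFS and OS is "Efficacy Evaluable", and the column for other populations is blank. The ITT entry in SAP section 3 is not completed, so the SAP defines no all-enrolled set.

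**The restricted set.** SAP section 3 builds it from "patients with measurable or evaluable disease at baseline who receive at least 1 dose of MLN9708 and undergo at least one post-baseline disease assessment". It adds back patients who left before a first assessment because of death or progression. Protocol 10.3 has the same definition ("The Efficacy Evaluable population will consist of all patients with measurable or evaluable disease at baseline") but assigns the set to no endpoint. Neither document says what makes disease evaluable.

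**Who can enter.** Protocol 3.1 requires "Achievement of at least a PR prior to allogeneic stem cell transplant", and protocol 3.2 excludes "Patients who have progressive disease when compared to pre-transplant staging". Nothing requires residual disease at entry.

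**The concern.** Different parts of the SAP lead to different denominators for the only two endpoints in its efficacy table. Nothing in the SAP says which one prevails.

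The restricted set is also a poor match for a maintenance trial. Under Appendix E, CR means negative immunofixation in serum and urine, no soft-tissue plasmacytoma and at most 5% marrow plasma cells. A patient who starts MLN9708 in CR or sCR would normally have no measurable disease, yet can still progress or die. Patients in PR would usually stay in. If patients in CR are left out and CR is favourable, the estimates no longer describe the patients who started maintenance, and both rates tend to be too low.

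The add-back clause could make this worse. It does not repeat the baseline-disease condition, so read literally it admits a CR patient who dies or progresses early while an event-free CR patient stays out.

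The post-baseline assessment condition is a smaller matter. It affects mainly OS, which needs no disease assessment. For PFS, a patient censored at Day 1 adds nothing to the curve.

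**Working it through.** **The plan's own figure.** Protocol 10.2 allows 3 cohorts × 6 = 18 patients in escalation and 20 in expansion: 18 + 20 = 38, as the synopsis states. The largest MTD group is 6 + 20 = 26. The documents give no target rate, test or power for PFS or OS, so there is no sample-size claim to reproduce.

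**The texts side by side.** The conflict needs no arithmetic: one part of the SAP names Efficacy Evaluable alone, and another names all enrolled plus the MTD group. The PFS censoring table gives modest further support. Its first row, "No baseline assessment", censors at first treatment, and a patient with no baseline assessment can hardly be shown to have disease at baseline.

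**Shift from leaving out CR patients.** The documents give no CR share, hazard ratio or survival rate, so these are assumptions:
- *f* = share in CR at entry
- *S* = 2-year rate in non-CR patients
- *HR* = hazard ratio, CR versus non-CR

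All dosed: *f*·*S*^HR + (1 − *f*)·*S*. Efficacy Evaluable: *S*. The difference, Efficacy Evaluable minus all dosed, is −*f*·(*S*^HR − *S*).

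| Endpoint | Case | *f* | *S* | *HR* | *S*^HR | Shift (points) |
|---|---|---|---|---|---|---|
| PFS | smallest | 0.3 | 0.5 | 0.7 | 0.616 | −3.5 |
| PFS | largest | 0.5 | 0.4 | 0.4 | 0.693 | −14.7 |
| OS | smallest | 0.3 | 0.7 | 0.7 | 0.779 | −2.4 |
| OS | largest | 0.5 | 0.6 | 0.4 | 0.815 | −10.8 |

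With *f* = 0.1, the PFS shift is −1.2 to −2.9 points. With *f* = 0 or *HR* = 1 it is zero.

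A second set of assumptions gives a similar picture. Take 2-year PFS of 40% in non-CR patients and 60–70% in CR patients, with 8 to 23 of 38 in CR (20–60%). The shift runs from −(8 × 0.20)/38 = −4.2 points to −(23 × 0.30)/38 = −18.2 points.

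**Add-back clause.** Take 15 of 38 in CR, with 2-year PFS of 70% in CR and 40% otherwise. All dosed: (15 × 0.70 + 23 × 0.40)/38 = 51.8%. Efficacy Evaluable without add-backs: 40%. If one or two CR patients with early events are added back: 9.2/24 = 38.3% or 9.2/25 = 36.8%.

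**Precision.** The 95% half-width at a rate of 50%, ignoring censoring, is 1.96·√(0.25/n). Losing 30–50% of patients gives:

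| Group | Full n | Half-width (points) | Reduced n | Half-width (points) |
|---|---|---|---|---|
| All | 38 | 15.9 | 27 to 19 | 18.9 to 22.5 |
| MTD | 26 | 19.2 | 18 to 13 | 23.1 to 27.2 |

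**Assessment condition, OS.** If *k* of 38 patients are dropped and their 2-year OS differs from the rest by 30 points (assumed), OS moves by (*k*/38) × 30: 0.8 points for *k* = 1 and 2.4 for *k* = 3. Few should be lost, because protocol 7.5 and Appendix D schedule a disease assessment at the end-of-treatment visit for early stoppers too.

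**The case against.** - **All enrolled may only mean all doses pooled.** The phrase is set against the MTD group, and protocol 10.4.2 makes a similar dose-level contrast for the biomarkers. An analyst could apply Efficacy Evaluable within each grouping. The reading is possible, but neither document states it.
- **A blank cell forbids nothing.** True: the column beside it names only the primary population. But the SAP does not then say which result is primary, all enrolled or Efficacy Evaluable.
- **Evaluable may mean assessable for progression.** That would keep CR patients in. Appendix E mentions CR at baseline, including the case "In case the only measurable disease in a patient with CR at baseline is the serum FLC level", so some CR patients might qualify on free light chains. This stands: the number lost is unknown and could be zero. It is also why the term needs a definition.
- **The censoring row is weak evidence.** The SAP is a checklist template, and the row has some use within Efficacy Evaluable. A patient assessed outside the 7-day baseline window, or added back after early death or progression, could fall under it. This largely stands; the conflict does not depend on the row.
- **The net direction is not fixed.** Leaving out CR patients lowers the estimates if CR is favourable. Dropping patients with no assessment raises OS if they do worse. This stands. At the smallest OS shift above, the two could cancel (2.4 points each way).
- **The shifts lie within sampling error, and no decision depends on them.** With 30–50% in CR, even the largest is below the 15.9-point half-width at n = 38. There is no test or threshold, so this limits the severity. It does not remove a systematic shift that the confidence interval does not reflect.

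**Conclusion.** The concern holds and should be fixed. The conflict over the analysis population is plain on the page and rests on no assumption. Followed as written, the endpoint table makes PFS and OS depend on baseline disease and on a later disease assessment. Neither is needed for OS, and PFS does not need baseline disease.

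The numerical effect is conditional. It requires that CR patients are treated as not evaluable and that CR is prognostic. Within the main assumed ranges it is 3.5 to 14.7 points for 2-year PFS and 2.4 to 10.8 points for 2-year OS, with wider intervals. It is zero if either condition fails. The MTD and the safety conclusions are untouched.

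**What to change.** 1. In the SAP endpoint table, set the population for both PFS and OS to all patients who received at least one dose, overall and at the MTD/MPD. This is the existing Safety set. It fits the time origin, because both endpoints start at first dose and a patient who is enrolled but never dosed has no start date.
2. Align the all-enrolled wording in SAP 1.2, protocol 10.4.2 and the synopsis with this, and state in protocol 10.3 that the set also serves PFS and OS. If the protocol is not amended, a line in the SAP recording the difference is enough.
3. Define evaluable disease and say whether CR or sCR at entry qualifies.
4. Keep Efficacy Evaluable for the response summaries (SAP Tables 10 and 11) or as a sensitivity analysis.
5. State that patients with no post-baseline assessment stay in. For PFS they are censored at Day 1 unless they die; for OS, if alive, at the date last known alive.

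The cost is wording only. No new data are needed, and it is best settled before results are seen.
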